9.3.2 Activities to be conducted at the Study Site

9.3.2.1 Screening Visit

The Screening visit must be performed within 28 days prior to dosing. The Investigator will maintain a log of subjects screened and indicate who was enrolled or excluded and the reason for exclusion ([Section 9.1.2](#)).

After obtaining informed consent and receiving a unique subject number, subjects will undergo a number of screening activities.

If possible, all screening activities should be conducted on the same day. At the Screening visit, the following activities/procedures will be performed:

- Informed consent obtained
- Assignment of subject number
- Review of eligibility criteria
- Demographics
- Medical/ophthalmic history including treatment history for DR/DME
- Temperature, height and weight
- 12 Lead ECG (prior to vital signs and blood draws)
- Vital signs:
 - sitting blood pressure and heart rate measurements
- Eye and Vision Exams:

- ETDRS BCVA
- slit-lamp biomicroscopy
- IOP
- dilated indirect ophthalmoscopy
- SD OCT
- fundus photography (and UWF fundus photography at select sub-study sites)
- fluorescein angiography (or UWF fluorescein angiography at select sub-study sites)
- Laboratory Procedures
 - serum pregnancy test for women of childbearing potential
 - hematology
 - clinical chemistry
- Concomitant Medication recording
- AE monitoring
- Dispense instructions and kit for subject to perform home fecal occult blood specimen collection

9.3.2.2 Baseline Period (Pre-Treatment, Day 1)

Eligible randomized subjects will be dosed at the Site on Day 1. At Baseline on Day 1, the following activities/procedures will be performed prior to any dosing of study medication:

- Interim medical/ophthalmic history
- Vital signs (to be performed within 2 hours prior to dosing and prior to blood draws):
 - sitting blood pressure and heart rate measurements
- Eye and Vision Exams:
 - ETDRS BCVA
 - slit-lamp biomicroscopy
 - IOP
 - dilated indirect ophthalmoscopy
 - ERG (at select sub-study sites)
 - OCT-A (at select sub-study sites)
- Laboratory Procedures
 - urine pregnancy test for women of childbearing potential (results must be known prior to dosing)
 - hematology
 - clinical chemistry
 - urinalysis
 - biomarker blood sampling
 - blood sampling for genetic analysis
- Concomitant Medication recording as needed
- AE monitoring

9.3.2.3 Treatment Period – Day 1

Following Baseline on Day 1, the following activities/procedures will be performed at the site

- Train subject on self-administration of study medication and diary completion. Distribute diaries.
- Subjects should eat a snack or meal and drink 1-2 glasses of fluid (See [Section 9.1.4](#)) within 1 hour to 30 minutes prior to dosing.
- Dose administration:
 - Subjects will self-dose the AM dose in the seated position and remain seated for 30 minutes following dosing.
- Sitting blood pressure and heart rate measurements will be conducted at 30 and 90 minutes after dosing. These assessments are to be conducted prior to any blood draws.
 - *If a subject develops symptoms of lightheadedness, presyncope, or of possible hypotension, consistent with medical practice it is recommended that the blood pressure and heart rate be re-measured and the subject placed in the supine position until symptoms resolve. The Investigator should also contact the study medical monitor.*
- PK blood sampling at 30 and 90 minutes after dosing. Sampling is to be conducted after blood pressure and heart rate measurements are completed.
- AE monitoring
- Concomitant Medication recording as needed
- Dispense 1 month supply of study medication kits and study medication diary.

9.3.2.4 Treatment Period – Day 7 (Week 1 Phone call)

- AE monitoring and AE recording since last visit
- Question subject regarding dosing compliance and whether they have questions or have experienced any problems related to the dosing of study medication

9.3.2.5 Treatment Period – Month 1 Visit (Week 4)

- Vital signs:
 - sitting blood pressure and heart rate measurements
- Eye and Vision Exams:
 - ETDRS BCVA
- Laboratory Procedures
 - clinical chemistry
- AE monitoring and AE recording since last visit
- Concomitant Medication recording as needed since last visit
- Collect returned used supplies and review medication use since last visit
- Dispense 1 month supply of study medication kits

9.3.2.6 Treatment Period – Month 2 Visit (Week 8)

- Vital signs:
 - sitting blood pressure and heart rate measurements
- Eye and Vision Exams:
 - ETDRS BCVA
- Laboratory Procedures
 - hematology

- clinical chemistry
- AE monitoring and AE recording since last visit
- Concomitant Medication recording as needed since last visit
- Collect returned used supplies and review medication use since last visit
- Dispense 1 month supply of study medication.

9.3.2.7 Treatment Period – Month 3 Visit (Week 12)

- Vital signs
 - sitting blood pressure and heart rate measurements
- Eye and Vision Exams:
 - ETDRS BCVA
 - slit-lamp biomicroscopy
 - IOP
 - dilated indirect ophthalmoscopy
 - SD OCT
 - fundus photography
 - ERG (at select sub-study sites)
 - OCT-A (at select sub-study sites)
- Laboratory Procedures
 - clinical chemistry
- AE monitoring and AE recording since last visit
- Concomitant Medication recording as needed since last visit
- Collect returned used supplies and review medication use since last visit
- Dispense 1 month supply of study medication kits

9.3.2.8 Treatment Period – Month 4 Visit (Week 16)

- Vital signs
 - sitting blood pressure and heart rate measurements
- Eye and Vision Exams:
 - ETDRS BCVA
- Laboratory Procedures
 - hematology
 - clinical chemistry
- AE monitoring and AE recording since last visit
- Concomitant Medication recording as needed since last visit
- Collect returned used supplies and review medication use since last visit
- Dispense 1 month supply of study medication kits

9.3.2.9 Treatment Period – Month 5 Visit (Week 20)

- Vital signs
 - sitting blood pressure and heart rate measurements
- Eye and Vision Exams:
 - ETDRS BCVA
- Laboratory Procedures

- clinical chemistry
- AE monitoring and AE recording since last visit
- Concomitant Medication recording as needed since last visit
- Collect returned used supplies and review medication use since last visit
- Dispense 1 month supply of study medication kits

9.3.2.10 Treatment Period – Month 6 Visit (Week 24)

Given that post-dose PK sample collection is included in this visit, subjects will be instructed to not administer their AM dose prior to their visit and to bring their AM dose along with other study medication in kits, as the AM dose will be administered in the clinic.

- Weight and Temperature
- 12 Lead ECG (prior to vital signs and blood draws)
- Vital signs
 - sitting blood pressure and heart rate measurements
- Eye and Vision Exams:
 - ETDRS BCVA
 - slit-lamp biomicroscopy
 - intraocular pressure
 - dilated indirect ophthalmoscopy
 - SD OCT
 - fundus photography (and UWF fundus photography at select sub-study sites)
 - fluorescein angiography (or UWF fluorescein angiography at select sub-study sites)
 - ERG (at select sub-study sites)
 - OCT-A (at select sub-study sites)
- Laboratory Procedures
 - urine pregnancy test for women of childbearing potential
 - hematology
 - clinical chemistry
 - urinalysis
- Subjects should eat a snack or meal and drink 1-2 glasses of fluid (See [Section 9.1.4](#)) within 1 hour to 30 minutes prior to dosing.
- Dose administration:
 - Subjects will self-dose AM dose in the seated position and remain seated for 30 minutes following dosing.
- Sitting blood pressure and heart rate measurements will be conducted at 30 and 90 minutes after dosing. These assessments are to be conducted prior to any blood draws.
- PK blood sampling at 30 and 90 minutes after dosing. Sampling is to be conducted after blood pressure and heart rate measurements are completed.
- AE monitoring and AE recording since last visit
- Concomitant Medication recording as needed since last visit
- Collect returned used supplies and review medication use since last visit

- Dispense 1-month supply of study medication kits
- Dispense instructions and kit for subject to perform home fecal occult blood specimen collection

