Study AKB-9778-CI-2002, a Phase 1b, open-label, MAD cohort study, was conducted to assess the safety, tolerability, pilot efficacy, PK and pharmacodynamic (PD) effects of 28-day repeat subcutaneous doses of AKB-9778 in subjects with DME. Four dose cohorts were administered 5, 15, 22.5 and 30 mg AKB-9778 BID, respectively. Twenty-six subjects in total were enrolled. Consistent with plasma exposure profiles in the healthy volunteer study, exposure in DME subjects increased with increasing dose levels of AKB-9778 with no evidence of significant accumulation. Absorption and elimination were rapid with an elimination half-life of approximately 1 hour. All AKB-9778 doses were generally well tolerated. There were no SAEs. Adverse events, consistent with the exaggerated vasodilatory pharmacology of AKB-9778, emerged at AKB-9778 doses of 22.5 and 30 mg BID and included dizziness, headache, and presyncope/syncope. These events were transient, usually occurred within the first hour after

dosing, and generally resolved within 5 minutes to one hour after onset. There were no clinically meaningful abnormalities or changes from baseline in safety laboratory tests (chemistry, hematology, and urinalysis), ECG parameters, vital signs or physical exams. In the 22.5 and 30 mg BID dose groups, consistent modest decreases in resting systolic BP (with corresponding modest increases in heart rate (HR)) were observed following dosing (30 mg > 22.5 mg). These effects were largely asymptomatic and transient, and the timing of the effects correlated with the rapid AKB-9778 absorption and elimination plasma concentration-time curve. Pilot efficacy evaluations, including assessments of retinal thickness and visual acuity, suggest that AKB-9778 exhibited biologic activity.

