All abnormal rhythms will be reviewed by the study physician for the presence of rhythms of potential clinical concern. The Investigator should utilize medical judgment in the reporting of AEs and SAEs as well as determination of additional cardiac work-up. A printed record of the tracing(s) of the clinically significant rhythm(s) will be made and retained with other source documents. An ECG will be performed at the Screening, Month 6, and Month 12 (EOT) visits.

- Vital Signs: Vital signs include blood pressure and heart rate. Vital sign assessments should be taken prior to blood draws when possible. The subject should be seated, with legs uncrossed and feet resting comfortably on the floor, for at least 5 minutes prior to measuring blood pressure and heart rate.
- ETDRS Best Corrected Visual Acuity (BCVA): Visual acuity of both eyes will be assessed using the ETDRS protocol at 4 meters.
- Slit Lamp Biomicroscopy: Slit-lamp biomicroscopy will include examination of the cornea, conjunctiva, anterior chamber, iris/pupil, lens, and eyelid of both eyes. Findings

will be graded as normal, abnormal not clinically significant, or abnormal clinically significant.

- Intraocular Pressure (IOP): IOP will be assessed with either applanation tonometry or tonopen; the method should be consistent throughout the study.
- Dilated Indirect Ophthalmoscopy: Dilated indirect ophthalmoscopy will be performed to assess the vitreous, macula, optic nerve, and peripheral retina of both eyes. Findings will be graded as normal, abnormal not clinically significant, or abnormal clinically significant.
- SD OCT: Spectral domain optical coherence tomography (SD OCT) will be utilized to assess retinal characteristics of both eyes. The OCT instrument type used throughout the study must be consistent for an individual subject. OCT imaging data will be transmitted to a central reading center for independent analysis. Detailed instructions for imaging and data transfers will be provided in the study-specific imaging manual.
- Fundus Photography: Modified 7-Field or 4-Wide Field color fundus photographs (including red free images) of both eyes will be taken to evaluate retinal anatomy. Photographs will be transferred to a central reading center. Detailed instructions for imaging and data transfers will be provided in the study-specific imaging manual.

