[E] ECGs will be performed after the subject rests in a supine position for approximately 5 minutes. ECGs should be taken prior to any vital sign assessments or blood draws.

[F] Assessments are conducted prior to any blood draws when possible. On Day 1, sitting BP and HR assessments will be conducted at Baseline (pre-dose) and at 30 and 90 minutes post-dose. On the Month 6 visit, sitting BP and HR assessments will be conducted prior to administration of the AM dose at the site and at 30 and 90 minutes after the AM dose.

[G] For sites participating in the UWF imaging sub study, at the Screening, Month 6 and Month 12 (EOT) visits, UWF fundus photographs will be obtained in addition to standard fundus photographs.

[H] For sites participating in the UWF imaging sub-study, UWF FA will be performed in lieu of FA.

[I] Performed only at sites with required equipment available.

[J] In women of child bearing potential, a serum pregnancy test will be conducted at the Screening visit. Prior to dosing on Day 1, a urine pregnancy test will be conducted on Day 1. At the Month 6 and Month 12 site visits, a urine pregnancy test will be conducted.

[K] HbA1C is conducted at Screening, Baseline, Month 6, and Month 12.

[L] eGFR will be determined on serum chemistry samples collected at the Screening, Baseline, Month 6, Month 9, and Month 12 (EOT) visits.

[M] UACR is measured at Baseline, Month 6, Month 9, and Month 12 (EOT) visits; subjects should refrain from heavy exercise 24 hours before these visits.

[N] Sites will distribute instructions and materials to subjects for home specimen collection and shipping to the central laboratory. Subjects will collect their specimens and are responsible for shipping to the clinical laboratory for testing; specimen collection and shipping should be conducted within one week following the site visit. Homecare nurses will review status of specimen collection and shipping with subjects.

[O] Subjects are to be instructed prior to the Month 6 visit to NOT take the AM dose prior to their visit and to bring their AM dose to the visit along with other study medication in kits, as the AM dose will be administered in the clinic on this visit. The post-dose PK sample collection on Day 1 and Month 6 is relative to time of dose administration. PK blood sampling is conducted at 30 and 90 minutes after dosing ± 10 minutes. PK blood samples are to be collected after vital signs are conducted.

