### **11.1.2 Electrocardiogram (ECG)**

Change from baseline for ECG parameters will be presented along with their associated 95% confidence intervals. Potentially clinically significant findings will also be presented based on the following categories:

- The proportion of patients obtaining treatment-emergent absolute QTcF values  $> 450$  ms and  $\leq 480$  ms;  $> 480$  ms and  $\leq 500$  ms; and  $> 500$  ms.
- The proportion of patients obtaining a QTcF increase from baseline values  $> 30$  and  $\leq 60$  ms; and  $> 60$  ms.
- The proportion of patients obtaining a QRS change from baseline  $> 25\%$  resulting in QRS  $> 120$  ms
- The proportion of patients obtaining a PR interval change from baseline  $> 25\%$  reaching a value  $> 220$  ms
- The proportion of patients obtaining a heart rate change from baseline  $> 25\%$  decrease resulting in a heart rate  $< 50$  beats per minute (bpm) and heart rate change from baseline  $> 25\%$  increase resulting in a heart rate  $> 100$  bpm

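### No planned ECG is timed to peak drug exposure: the Month 6 ECG precedes the dose and the Month 12 ECG is not tied to one

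*Protocol*

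**What the plan says.** On the number of ECGs, Protocol 9.2.1 states: "An ECG will be performed at the Screening, Month 6, and Month 12 (EOT) visits". Day 1 has blood pressure, heart rate and PK after dosing (9.3.2.3), but no ECG.

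For Month 6, Protocol 9.3.2.10 holds back the home injection: "subjects will be instructed to not administer their AM dose prior to their visit". The dose is then given in clinic. Appendix A sets the order. Footnote [E]: "ECGs should be taken prior to any vital sign assessments or blood draws". Footnote [F]: "On the Month 6 visit, sitting BP and HR assessments will be conducted prior to administration of the AM dose at the site". After the dose, blood pressure, heart rate and PK are taken at 30 and 90 minutes; the ECG is not repeated.

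For Month 12, Protocol 9.3.2.16 places the ECG before vital signs and blood draws and gives no link to a dose. Footnote [P] names only Day 1 and Month 6 as visits with dosing at the site. No text says whether that morning's home injection is to be taken or held.

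On kinetics, Protocol 4.3 gives a Tmax of roughly 15 to 30 minutes and a half-life of roughly 1 to 2 hours in healthy volunteers. For subjects with DME it says: "Absorption and elimination were rapid with an elimination half-life of approximately 1 hour", without significant accumulation.

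SAP 5.5 analyses ECG heart rate, PR, QRS and QTcF at weeks 24 and 48. SAP 11.1.2 adds outlier categories, the first being "The proportion of patients obtaining treatment-emergent absolute QTcF values" in three bands. Neither section mentions time since dose.

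**The concern.** The protocol treats this drug's haemodynamic effects as following its plasma curve, and it times blood pressure, heart rate and PK accordingly. At the same Month 6 visit the ECG is placed on the other side of the dose. Month 12 does not make up for this, and for subjects who stop early the end-of-treatment assessments come after medication has stopped (Protocol 7.6).

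ECG change is a listed safety endpoint (Protocol 5.6.3) under a secondary objective. If the summaries show nothing, a reader of the study report may take that as evidence of no conduction or repolarisation effect at 15 mg, although no recording was aimed at the time of highest concentration. Also, no ECG sits beside a post-dose PK sample, so ECG intervals could contribute little to the exploratory exposure-safety work.

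**Working it through.** The plan states no exposure figure for the ECG time, so there is none to reproduce.

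**Step 1: order of events at Month 6.** Footnote [E] puts the ECG before any vital signs. Footnote [F] puts the first vital signs before the AM dose. So the ECG precedes the dose, and the last injection was the previous evening's.

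**Step 2: drug remaining at that ECG.** Inputs: half-life h of 1 to 2 hours (Protocol 4.3); morning and evening dosing (Protocol 8.3.5). The gap in hours is not stated; I assume t = 12, with a range of 10 to 14. The fraction remaining is 2^(−t/h). For example, 2^(−12/1) = 1/4096 = 0.024% and 2^(−12/2) = 1/64 = 1.6%.

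| Half-life | 10 h | 12 h | 14 h | 24 h |
|---|---|---|---|---|
| 1 h | 0.098% | 0.024% | 0.006% | <0.001% |
| 2 h | 3.1% | 1.6% | 0.78% | 0.024% |

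The 24-hour column applies to the QD arm if its active syringe is the AM one. If the active syringe is the PM one, the 10- to 14-hour columns apply. The documents do not say which is active.

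**Step 3: cross-check as a percentage of Cmax.** This assumes one compartment with first-order absorption. C(t) is proportional to exp(−ke·t) − exp(−ka·t), with ke = ln 2 / h and ka solved from ln(ka/ke)/(ka − ke) = Tmax.

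| Half-life, Tmax | ka (per h) | 0.5 h | 1 h | 1.5 h | 2 h | 4 h | 12 h |
|---|---|---|---|---|---|---|---|
| 1 h, 15 min | 12.15 | 88.9 | 63.1 | 44.6 | 31.5 | 7.9 | 0.03 |
| 1 h, 30 min | 4.38 | 100 | 81.9 | 59.2 | 42.0 | 10.5 | 0.04 |
| 2 h, 15 min | 15.57 | 93.7 | 78.9 | 66.3 | 55.8 | 27.9 | 1.7 |
| 2 h, 30 min | 6.07 | 100 | 88.9 | 75.0 | 63.1 | 31.5 | 2.0 |

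The existing 30-minute point falls at about 89% to 100% of Cmax, and the 12-hour point at about 0.03% to 2.0%.

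**Step 4: Month 12.** If the subject injected at home 1, 2 or 4 hours before the ECG, the same table gives about 63–89%, 32–63% or 8–32% of Cmax. If that morning's dose was not taken, the figure is about 0.03–2.0%. Exposure at this ECG can therefore be almost anything, and is near peak only by chance.

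**Step 5: room for a post-dose ECG.** Protocol 9.3.1 allows ±10 minutes for PK and ±20 minutes for blood pressure and heart rate. The first PK sample is due by 30 + 10 = 40 minutes, and the second vital signs may start at 90 − 20 = 70 minutes. That leaves 30 minutes. Protocol 9.2.1 asks for about 5 minutes supine before the ECG and at least 5 minutes seated before blood pressure, so both fit. An ECG done by 60 minutes would be at no less than about 63% of Cmax.

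**The case against.** The strongest reply is that the plan breaks no promise. It never says the ECG endpoint targets peak exposure, the objective is safety over 12 months, and an ECG change that persists between doses remains detectable. The effects known to follow the plasma curve are blood pressure and heart rate, and both are measured at 30 and 90 minutes on Day 1 and at Month 6 alongside PK. Protocol 4.3 reports no meaningful ECG findings in two earlier studies, at up to 80 mg as a single dose, 60 mg twice in one day, and 30 mg BID for 28 days. All of this stands, and it limits the gap to PR, QRS, QTcF and rhythm. The earlier results do not close it, because the protocol does not give the ECG timing in those studies and the Investigator's Brochure is not before us.

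Protocol 9.2.1 also softens the ECG order to apply when possible. That tolerates an out-of-order ECG but does not plan a post-dose one.

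Three stronger readings are tempting, and the documents do not support them:
- A reader might infer that the ECG endpoint cannot show any drug effect. Month 12 visits are to be in the morning and nothing holds the AM dose, so some subjects may have material exposure.
- A reader might infer that SAP 11.1.2 labels every ECG category treatment-emergent. The term appears only for absolute QTcF; the other categories are changes from baseline.
- A reader might infer that pairing ECG with PK was promised. Protocol 11.8 speaks of selected safety parameters, and SAP 12 says such analyses may be done.

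**Conclusion.** The point holds as a limit on what the ECG results are designed to detect. By plan, the Month 6 ECG is recorded with about 0.02% to 1.6% of the drug remaining (0.006% to 3.1% if the gap is 10 to 14 hours), and the Month 12 ECG at an uncontrolled time since dose. The PR, QRS and QTcF summaries in SAP 11.1.2, and the rhythm review in Protocol 9.2.1, are therefore not set up to find a concentration-driven effect.

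A reader might go further and call a null ECG result uninformative or falsely reassuring. That is too strong: a persistent effect could be seen, Month 12 may catch some exposure, and the documents show no ECG signal.

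The conclusion rests on the half-life in Protocol 4.3 and the assumed overnight gap, and does not change anywhere in the range shown. The efficacy analyses are untouched. It merits a change because the change is cheap.

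**What to change.** **Protocol 9.3.2.10 and Appendix A footnote [E].** Move the single Month 6 ECG to after the in-clinic AM dose, near the 30-minute point. Place it directly after the 30-minute sitting blood pressure, heart rate and PK sample, so that the supine rest does not disturb those readings. State this as an exception to the rule that ECGs come before vital signs and blood draws. Keep the Screening ECG as the drug-free baseline.

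**Seated rule.** Protocol 9.3.2.10 and footnote [P] ask subjects to stay seated for 30 minutes after dosing without exception, while 8.3.5 and 9.1.4 exempt study assessments. PK may be drawn from 30 − 10 = 20 minutes, so an ECG straight afterwards could fall inside that period. These passages must be reconciled.

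**SAP 11.1.2.** State that Month 6 ECGs are post-dose. Present Month 12 ECGs by time since last dose, from the diary injection time and the ECG clock time. The clock time is not among the ECG results listed in Protocol 9.2.1, so confirm that it is captured. State which QD syringe, AM or PM, is active and interpret that arm accordingly: if it is the PM one, the moved ECG follows placebo in that arm and only the BID arm gives near-peak information.

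**Cost.** Protocol and SAP wording and a re-ordered visit, with the number of ECGs unchanged. The Month 6 trough ECG, the only one at a controlled time since dose, is given up, and there is a brief posture change after dosing. If Month 6 visits have already taken place in the current order, the SAP should instead label those ECGs as pre-dose.
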